4.2.2 Handling of Incomplete Dates in Context of Concomitant Medications

Any medications with incomplete start and/or end dates will be handled according to the following rules for classification as prior and concomitant and for the calculation of relative study days. Such imputations will only be performed for these classifications and calculations; in the listings all data will be shown as recorded on the eCRF.

Imputation of Partial Start Dates:

- If only the month and year are specified and the month and year of first dose of study medication are not the same as the month and year of the start date, then use the 1st of the month

- If only the month and year are specified and the month and year of first dose of study medication are the same as the month and year of the start date, then use the date of first dose of study medication
- If only the year is specified, and the year of first dose is not the same as the year of the start date of study medication, then use January 1 of the year of the start date
- If only the year is specified, and the year of first dose is the same as the year of the start date, then use the date of first dose of study medication
- If the start date is completely unknown and the stop date is unknown or not prior to the date of first dose, then use the date of first dose of study medication

Imputation of Partial Stop Dates:

- If only the month and year are specified, then use the last day of the month
- If only the year is specified, then use December 31 of that year
- If the stop date is completely unknown, do not impute the stop date

In the event of ambiguity or incomplete data which makes it impossible to determine whether a medication was concomitant or not, the medication will be considered as concomitant.

4.2.3 Handling of Adverse Events with Missing Data

Any AEs with incomplete onset and outcome (end) dates/times will be handled according to the following rules for classification as treatment-emergent. Such imputations will only be performed for these classifications; in the listings all data will be shown as recorded on the eCRF.

Imputation of Partial Onset Dates:

- If only the month and year of onset are specified and the month and year of first dose of study medication are not the same as the month and year of onset, then use the 1st of the month
- If only the month and year of onset are specified and the month and year of first dose of study medication are the same as the month and year of onset, then use the date/time of first dose of study medication
- If only the year is specified, and the year of first dose of study medication is not the same as the year of onset, then use January 1 of the year of onset
- If only the year is specified, and the year of first dose of study medication is the same as the year of onset, then use the date/time of first dose of study medication
- If the onset date of the AE is completely unknown, then use the date/time of first dose of study medication

Imputation of Partial End Dates:

- If only the month and year are specified, then use the last day of the month
- If only the year is specified, then use December 31 of that year

- If the AE resolved and the resolution date is completely unknown, then do not impute the resolution date
- If the onset time of the event is unknown, impute it as 00:00 unless the known part of the onset date is the same as the date of first dose of study medication; in this case impute the time of first dose of study medication

With respect to AEs, events with missing intensity will be assumed to be severe. Events with missing relationship to study medication per the investigator will be assumed to be related.

Data handling for worsened AEs is provided below. The standard AE CRF has the outcome of “worsened” to be used when there is an increase in the intensity of an AE. The definition of “worsened” is when the AE is still present but at a heightened intensity. CRF instructions dictate to complete a new AE screen with the event term of the worsened event.

Note that the outcome of “worsened” is not allowed terminology within the CDISC standards. In the SDTM.AE, the data is mapped to the outcome “Not Recovered/Not Resolved”. The outcome of “Worsened” will be kept in SDTM.SUPPAE. For subject data listings, the convention will be to use the mapped SDTM terminology of “Not Recovered/Not Resolved”.

4.2.4 Handling of Study Medication with Missing data

No imputation should be performed for missing start dates of study medication. This field on the CRF should not be partial or missing.

If a subject has missing last administration information from the Study Termination CRF page, the last available treatment date with nonzero total daily dose from Drug Dosing Log will be used for last administration date if it is not the same as the first administration date of the subject. If the subject does not have any available treatment date or the last available treatment date is the same as the first administration date from Drug Dosing Log and is missing last administration information from the Study Termination CRF page, the last contact date from CRF is used for the last administration date.

Imputed date of last dose dates should only be used for calculation of the duration of exposure. The date as recorded on the CRF should be presented in subject data listings (no imputed dates should be included in subject data listings).

4.3 Interim Analyses and Data Monitoring

No formal interim analysis is planned for this study. For regulatory purposes, two planned data cut-offs will be made when the final subject who completes the Evaluation Period reaches Visit 13 and Visit 16 in order to obtain 6-month and 12-month exposure data, respectively. All the efficacy and safety analysis planned in the protocol will be performed for NDA submission using the interim cut-off data followed by additional cut-off and/or final analysis for long-term follow-up evaluation.

In addition to above, an interim analysis (IA) was performed for providing PMDA with the latest information to discuss if the study can be discontinued and the application method can be changed to extrapolation strategy based on the results of the IA, which is based on the suggestion at the consultation meeting with PMDA held on [REDACTED] The IA was performed according

to the eCRF snapshot on 04 Jun 2021, in which the data cut-off date was 30 Apr 2021.

4.4 Multicenter Studies

Since it is expected that there will be only a few subjects per age category and center combination, there are no plans to summarize data by age category and center. Summary tables will be presented pooled for all centers.

4.5 Multiple Comparisons/Multiplicity

If the primary analysis of the primary variable (median percent reduction for adjunctive therapy) at Study Visit 6 is not significant, the statistical testing will stop. If testing at Study Visit 6 is significant, the analysis will be repeated for Study Visit 4. If testing at Study Visit 4 is also significant, the analysis will be repeated for Study Visit 5. In that case, the second and the third analyses are also regarded as confirmatory as due to the hierarchical testing procedure no alpha adjustment is needed.

4.6 Use of an Efficacy Subset of Subjects

No additional efficacy subset is used.

4.7 Active-control studies intended to show equivalence

No comparator and no testing for equivalence in this study, hence this section is not applicable for this study.

4.8 Examination of Subgroups

In this study 4 age categories will be investigated: 1 month to <6 months, 6 months to <1 year, 1 year to <2 years, and 2 years to <4 years. For the primary efficacy variable the data of the two youngest age categories will be pooled and data of the primary efficacy variable will be summarized by the so-obtained 3 age-categories and overall.

Note: for the age classification, the age at entry into study is used (Section 3.2.5.3).

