5.1.3 Second Period

Subjects who complete the First Period will have a visit every 4 weeks \pm 7 days relative to Visit 3 for the first 6 months of administration and then every 12 weeks \pm 14 days thereafter. Subjects will continue to receive LEV 14 to 42mg/kg/day in subjects aged 1 month to <6 months or LEV 20 to 60mg/kg/day for subjects aged \geq 6 months <4 years at the discretion of the Investigator.

When subjects aged <6 months at the time of study enrollment reach 6 months of age, they can take a maximum of LEV 60mg/kg/day.

A final visit will be required 2 weeks \pm 7 days after the final dose of LEV, or sooner if the subject will continue LEV (prescribed by the primary care provider as commercial LEV) after study completion.

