8.1.2.2 Visit 4 (Week 2)

- Obtain vital sign measurements (blood pressure, pulse rate, and body temperature)
- Collect blood samples for safety laboratory assessments
- Collect blood samples for LEV plasma level
- Record body weight
- Record concomitant medications (AEDs and non-AEDs) and medical procedures
- Record AEs
- Collect seizure count from DRC
- Dispense/collect DRC
- Study drug compliance
- Confirm if fallback option is necessary and reason(s) to decrease the dosage
- Contact IVRS/IWRS
- Dispense/collect study drug

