8.2.7 Visit 13 (Week 26)

- Obtain vital sign measurements (blood pressure, pulse rate, and body temperature)
- Collect seizure count
- Collect blood samples for safety laboratory assessments

- Collect blood sample for LEV plasma level
- Record body weight and height
- Record concomitant medications (AEDs and non-AEDs) and medical procedures
- Record AEs
- Dispense/collect study drug
- Study drug compliance
- Perform ECG
- Contact IVRS/IWRS
- Dispense/collect DRC

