3.2.5.2 Adjusted Age

Pre-Term birth will be accounted for by using the adjusted age which is defined as

- $[(\text{Date} - \text{Date of Birth}) - (36 - \text{number of weeks pre-term}) \times 7] / 30.4375$
for subjects of chronological age < 12 months and
- Chronological age, otherwise

If not specified otherwise, adjusted age at the date of the assessment is used for all analyses.

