3.2.5.3 Age at Entry Into Study

The adjusted age at entry into study is defined as the adjusted age at the screening date. This is also referred to as “Age at entry into study”

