9.1.2 Tables and Figures

Descriptive statistics of LEV observed and dose-normalized plasma concentrations will be summarized per defined time window post-dose by age category (1 month \leq Age $<$ 6 months, 6 months \leq Age $<$ 1 year, 1 year \leq Age $<$ 2 years, 2 years \leq Age $<$ 4 years) and dose level per administration (10mg/kg, 20mg/kg, 30mg/kg in aged subjects of 6 months and above, 7mg/kg, 14mg/kg, 21mg/kg in aged subjects less than 6 months) in PK-PPS_A and PK-PPS_M. The statistics are calculated only if at least 2/3 of the individual data at a specific sampling point are above or equal to the LLOQ.

Scatter plots of LEV observed plasma concentrations vs. time after last dosing will be presented by age category and dose level. Scatter plots for LEV observed plasma concentrations vs time after last dosing by dose level will be superposed with different symbols in a single graph for each age category.

Scatter plots of LEV observed plasma concentrations vs. time after last dosing will be presented by age category and dose group. Scatter plots for LEV observed plasma concentrations vs time post dose by dose group will be superposed with different symbols in a single graph for each dose group. The dose groups are defined as:

- low dose group, 7mg/kg in aged subjects less than 6 months and 10mg/kg in aged subjects of 6 months and above;
- middle dose group, 14mg/kg in aged subjects less than 6 months and 20mg/kg in aged subjects of 6 months and above;

- high dose group, 21mg/kg in aged subjects less than 6 months and 30mg/kg in aged subjects of 6 months and above

Scatter plots of LEV dose-normalized plasma concentrations vs. time after last dosing will be presented by age category and dose level. Scatter plots for LEV dose-normalized plasma concentrations vs time after last dosing by dose level will be superposed with different symbols in a single graph for each age category.

Another scatter plot for LEV dose-normalized plasma concentrations vs time after last dosing will be presented by age category and AED category with different symbols in a single graph.

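### The SAP does not say whether age at entry or age at sampling governs the PK age categories, and neither rule fits the planned PK tables as written

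*SAP*

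**What the plan says.** SAP 4.8 lists four age categories (1 month to <6 months, 6 months to <1 year, 1 year to <2 years, 2 years to <4 years) and adds: "Note: for the age classification, the age at entry into study is used (Section 3.2.5.3". SAP 3.2.5.3 defines that age: "The adjusted age at entry into study is defined as the adjusted age at the screening date". SAP 3.2.5.2 sets a different general rule: "If not specified otherwise, adjusted age at the date of the assessment is used for all analyses".

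For PK, SAP 9.1.2 says: "Descriptive statistics of LEV observed and dose-normalized plasma concentrations will be summarized per defined time window post-dose by age category". The categories are the four of SAP 4.8. The table is also split by dose level per administration: "7mg/kg, 14mg/kg, 21mg/kg in aged subjects less than 6 months", and 10, 20 and 30 mg/kg from 6 months upwards. SAP 9.1.1 normalises concentrations to 7 mg/kg below 6 months and to 10 mg/kg from 6 months. Normalised values are then overlaid on N01223 data (normalised to 10 mg/kg for body weight under 50 kg) and, by age category, on profiles simulated from the N01288 model. Nothing in SAP section 9 says which age is meant.

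Protocol section 8 schedules plasma levels at Visits 4, 5 and 6 (for Visit 4: "Collect blood samples for LEV plasma level") and at Visits 8, 10, 11, 12 and 13. The last of these is Week 26: "Collect blood sample for LEV plasma level". On dosing, protocol 5.1.3 says: "When subjects aged <6 months at the time of study enrollment reach 6 months of age, they can take a maximum of LEV 60mg/kg/day".

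**The concern.** The youngest category spans five months of age and sampling lasts about six months, so infants cross the 6-month boundary while they are being sampled. That boundary matters for PK. Protocol 5.4 sets a separate dose range below it, about 70% of the range for older children, on the basis of the N01288 population PK analysis.

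If category is frozen at entry, concentrations labelled 1 month to <6 months partly describe older infants, and the N01288 and N01223 overlays for that group mix the two sides of the boundary. If category follows age at sampling, some samples fit no cell of the planned table. With the rule unstated, two programmers could produce materially different PK tables from the same SAP, in a group with a planned minimum of 5 subjects.

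**Working it through.** The plan states no figure for the age mix of PK samples, so there is none to reproduce.

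**Inputs**
- Sampling weeks 2, 4, 6, 10, 14, 18, 22 and 26 (visit lists in protocol section 8).
- 30.4375 days per month (SAP 3.2.5.1).
- Visit 1 falls 2 to 9 days before first dose (protocol 8.1.1.1); age at entry is taken there.
- Minimum of 5 subjects per age group (protocol 5.1.5).
- Assumption: entry age uniform on 1 to <6 months. The documents give no distribution, so it is varied below.
- Assumption: adjusted age equals chronological age for a term infant. The formula in SAP 3.2.5.2 does not give this when read literally (last step).

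**If entry age governs**

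Months elapsed at week w = 7w / 30.4375. Share of youngest-category samples taken at 6 months or older = min(1, months elapsed / 5).

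| Week | 2 | 4 | 6 | 10 | 14 | 18 | 22 | 26 |
|---|---|---|---|---|---|---|---|---|
| Share | 9% | 18% | 28% | 46% | 64% | 83% | 100% | 100% |

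- Mean of the eight: 4.484 / 8 = 56%. Adding the screening gap gives 57% (2 days) to 60.5% (9 days).
- First Period (Weeks 2, 4, 6): 0.552 / 3 = 18%, or 24% with a 9-day gap.
- Second Period (Weeks 10 to 26): 3.932 / 5 = 79%, or 82% with a 9-day gap.
- Week 22 is 22 × 7 / 30.4375 = 5.06 months and Week 26 is 5.98 months. Even an infant entering at exactly 1 month therefore gives 2 of 8 samples (25%) at 6 months or older. Entry at 3.5 months gives 50%, at 5 months 75%, at 5.9 months 100%.
- Other entry-age spreads: 40% (uniform 1 to 4 months), 43% (triangular, mode 1 month), 54% (mode 3.5), 69% (mode 6). Confining entry to one half of the band gives 37% (1 to 3.5 months) or 75% (3.5 to 6 months).
- If 30% or 40% of infants do not enter the Second Period: 51% or 49%.
- Other schedules: 48.5% with two samples at Visits 4 and 6, as before Amendment 3; 51.6% for earlier video-EEG failures; 49.8% if the Week 0 mark in protocol Table 5–1 is counted.
- With 5 infants there are 5 × 8 = 40 scheduled samples. At 56%, about 22 were taken at 6 months or older and about 18 before.

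Normalised value = observed / actual dose × reference dose. If entry age also sets the reference dose, a sample from an infant now 6 months or older is multiplied by 7 instead of 10. Since 7 / 10 = 0.70, the value is 30% lower. An infant who has moved to 10, 20 or 30 mg/kg per administration has no row in the youngest category.

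**If age at sampling governs**
- Protocol 5.1.3 permits the higher maximum after 6 months but does not require a change. An infant past 6 months still on 7, 14 or 21 mg/kg has no row among 10, 20 and 30 mg/kg.
- A child entering after about 4 − 5.98/12 = 3.5 years turns 4 by Week 26 and has no age category.

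These gaps do not depend on any entry-age distribution.

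**Adjusted-age formula**

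SAP 3.2.5.2 subtracts (36 − weeks pre-term) × 7 days for subjects under 12 months. At 0 weeks pre-term that is 252 days, or 252 / 30.4375 = 8.28 months. Read literally, a term infant of 6 months has an adjusted age of −2.28 months, and every term infant under 12 months falls below 12 − 8.28 = 3.72 months. Any rule built on adjusted age inherits this.

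**The case against.** The best reply is that the SAP does not fix PK age at entry. Section 9 is silent, SAP 3.2.5.2 makes age at assessment the default, and the dose strata and normalisation are worded in terms of subjects below 6 months, which can be read as current age. That stands: a reader might infer from SAP 4.8 that entry age is settled for PK, and the documents do not go that far. The entry-age reading is still natural. SAP 4.8 names the same four categories, and where the SAP wants age at the visit it says so (12.3.1, 12.3.2, 12.5, 12.6); section 9 has no such note.

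It also stands that the two sets of failures are alternatives. The older samples in the youngest category arise under entry age; the missing rows for children turning 4 and for infants still on the younger dose levels arise under age at sampling. They should not be added together.

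A reader might further infer that the PK objective goes unanswered for the youngest group, or that more than half of its samples are certain to be misplaced. Neither is supported. The objective covers 1 month to <4 years across both periods, with no separate objective below 6 months and no PK hypothesis test. Under entry age, about 76% to 82% of First Period samples in the category would still come from infants under 6 months. Dose-level strata and scatter plots separate some of the rest. Birth dates (SAP 6.1.3) and sampling times (SAP 9.1.3) allow reclassification, although the PK listing itself shows age in years and population PK is planned only as needed (protocol 13.5.2). The share above one half depends on the entry-age distribution and on near-complete Second Period sampling.

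**Conclusion.** The concern holds as an unresolved conflict between SAP 3.2.5.2 and 4.8 that section 9 does not settle, with PK tables that fit neither rule. Under entry age, the share of youngest-category samples taken at 6 months or older is about 56% with uniform entry and complete sampling, about 40% to 70% under other entry-age assumptions, 18% to 24% in the First Period and about 79% in the Second. The 30% reduction in normalised values applies only if entry age also sets the reference dose. Under age at sampling there is no such mixing, but some samples have no row.

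The consequence is blurred descriptive PK results and blurred N01288 and N01223 overlays for the youngest group, mainly in the Second Period. The primary efficacy analysis does not use these PK tables. The point is worth correcting because the change is small and the 6-month boundary is the one on which the separate dose range rests.

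**What to change.** Correct the adjusted-age formula in SAP 3.2.5.2 first, so that a term infant receives no adjustment. Then, in SAP 9.1.1 to 9.1.3:

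- State that age at the sampling date governs the PK age category, the reference dose for normalisation and the N01288 overlay.
- Assign dose level by the actual mg/kg per administration, regardless of age band, so that every sample has a row.
- Add a row for samples taken at 4 years or older.
- State that the entry-age note in SAP 4.8 does not apply to PK. Leave the age-at-assessment rules for laboratory, vital-sign and weight criteria (SAP 12.3.1, 12.3.2, 12.5, 12.6) unchanged.

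The cost is SAP wording and one derivation change; birth dates, sampling times and doses are already collected. The small downside is that one infant can contribute samples to two age categories, which a table footnote can state.

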5 STUDY POPULATION CHARACTERISTICS

5.1 Subject Disposition

Summary tables and listings will be presented for subjects on adjunctive therapy and for subjects on monotherapy, separately.

Disposition related tables cover a presentation of screen failure reasons, frequencies of completed and discontinued subjects including reason for discontinuation overall and by video-EEG status (video-EEG failures and video-EEG non-failures for subjects enrolled prior to Protocol Amendment 3 and subjects enrolled following Protocol Amendment 3), attendance at visits and periods, study duration as well as analysis sets. In addition, information on number of subjects enrolled (ie, Enrolled Set), and being in the Safety Sets, Full Analysis Sets, and

Pharmacokinetic Per-Protocol Sets is presented overall and by investigator site together with the date of first subject in and last subject out.

The following listings will be provided: study eligibility criteria text; subjects who did not meet study eligibility criteria; subject disposition; study discontinuation; visit dates; study periods; and subject analysis sets.

5.1.1 Definitions and Derivations

5.1.1.1 Subject Status

Subject status regarding completion is taken from the Study Termination CRF.

5.1.1.2 Last Administration of Study Medication

Missing values for date of last administration of study medication are imputed as specified in [Section 4.2.4](#).

5.1.1.3 Time to Discontinuation from Study

An event in the sense of the variable Time to Discontinuation from Study is observed if for a subject on the Study Termination CRF Subject status at study termination is “Dropout”.

In case of an event,

Time to Discontinuation from Study [months] =
12 x (Date of premature study termination [Study Termination CRF] -
date of enrolment) / 365.25.

This observation is not censored.

In case of no event,

Time to Discontinuation from Study [months] =
12 x (Date of last visit – date of enrolment) / 365.25.
This observation is censored.

5.1.1.4 Period Started/Ended

A subject is regarded to have started / ended period as described in [Section 3.2.1.2](#).

5.1.1.5 Duration of a Period

The duration of a period is not shown in context of disposition. The duration of a period is used as the duration of exposure to study medication, see [Section 3.2.7](#).

